## **Evaluation of interventions to support status disclosure to male partner and viral suppression among women living with HIV**

### Status disclosure

In PMTCT, status disclosure has been shown to significantly increase ART adherence and viral suppression (VS). In an observational study of 150 PWLHIV in southwestern Uganda with over 4 years of follow-up, women who disclosed to their partner were 4.5-fold more likely to achieve VS (82). Similar observations were made among 170 Nigerian PLWHIV; the most important motivator for ART adherence was desire to protect the infant; significant factors associated with VS were disclosure to their partner and having a treatment partner (83).

A systematic review of status disclosure by African PLWHIV reported factors associated with HIV disclosure for the woman (younger age, first pregnancies, knowing someone with HIV, lower levels of internalized stigma, lower levels of avoidant coping), partner (prior history of HIV testing, higher education), partnership (no history of domestic violence, financial independence), and household (higher quality housing, residing without spouses or extended family (84). A review of HIV status disclosure interventions in low and middle income countries found 4 studies among PLWHIV, most of which involved support groups with 4 to 10 sessions; the studies had mixed results on disclosure outcomes but were limited by small sample sizes and high attrition (85). A randomized trial of a problem-solving group intervention for depression and disclosure among Tanzanian PLWHIV showed that depression decreased and there was a trend towards increased HIV disclosure in the intervention arm (56% vs 46%; OR 1.2,  $p=0.19$ ), but it was limited by 30% of women not being exposed to the intervention and high drop-out (86). There is a clear need for evidence-based and feasible disclosure support interventions for African PLWHIV.

Problem-solving therapy (PST) is an appealing approach for pregnant women facing psychological and behavioral challenges related to HIV status disclosure and motivation to continue ART post-partum because it aims to develop actionable solutions and improve coping around adherence issues (87). PST is recommended by the WHO for treating common mental health disorders in resource-limited settings given its flexibility, low cost, and lay counselor delivery. Core components include problem identification, generation of alternative solutions, decision-making, and solution implementation (88).

To address the challenges of status disclosure for PWLHIV in our previous study called Obumu, we piloted PST delivered through monthly peer support groups with a mix of women who had, and had not, disclosed their status to their partners. Peer support groups were facilitated by peer mothers (expert clients with HIV who have been trained in ART adherence counseling and hired by the Ugandan MoH) and an Obumu staff member. Among the 157 PWLHIV enrolled in Obumu who participated in peer support groups (8-17 women per group), women reported that encouragement and suggestions from their peers motivated and helped them find ways to approach their partner about HIV testing and disclose their HIV status, providing preliminary data about the promise of this approach to support HIV status disclosure in this population.

In Kingasa, we will offer PST, delivered by trained peer mothers who participated in Obumu and have experience with status disclosure. Mothers will be selected and trained by nurse midwives who have expertise in PST and counseling about status disclosure from Obumu. Mothers who have enrolled in Kingasa will be offered problem-solving therapy one-on-one at antenatal visits as well as through group sessions. Acceptability and status disclosure pre- and post- problem solving therapy will be evaluated.

### POC HIV Viral Load

Based on our preliminary analysis of women in Obumu who have had a 6 and/or 12-month post-partum visit, 24% and 34%, respectively, have not had a viral load recorded (compared to 98% at enrollment). Among postpartum who have had a viral load obtained, 20-22% had detectable viral load. Missing viral

loads and detectable viral load among postpartum women, combined with not receiving their results until their next postpartum visit indicates that a substantial proportion of postpartum women living with HIV are not receiving the benefit of viral load monitoring and prompt ART adherence counseling. Additionally, DNA-PCR coverage for early infant diagnosis (EID) in Uganda is suboptimal; only 64% of HIV exposed infants (HEI) received an initial DNA PCR test delivery, < 55% of HEI receive a virological test within 2 months of birth, and only 28% receive their final rapid test at 18 months of age (89).

The feasibility of POC VL with Xpert HIV-1 VL at the time of delivery combined with neonatal diagnosis EID using the Xpert HIV-1 EID has been demonstrated in South Africa (90). Approximately 75% of mothers and newborns received the maternal POC VL and EID prior to discharge (91). A field evaluation of POC EID for neonatal diagnosis in South Africa showed good performance, improved rates of results returned to mothers (96% compared to 89% of lab-based EID), and reduced time to ART initiation for infected neonates (5 days earlier for infants diagnosed with the Xpert HIV-1 EID). Additional evaluation is needed in non-tertiary obstetric units and health centers in terms of feasibility of introducing POC maternal VL and EID in terms of implementation aspects, coverage, turn-around time, and results return before women are discharged after delivery.

Our co-investigator, [name], demonstrated in the STREAM study among 390 PLWHIV in KwaZulu-Natal South Africa, that POC VL using the Cepheid Xpert HIV-1 viral load assay with same day adherence counseling by nurses (i.e., task shifting) was associated with a 13.9% increase in viral suppression and retention in care compared to the control group, which received VL results and counseling at their next visit.(26) There were no adverse events, both patients and providers preferred POC testing over lab-based testing, and POC VL testing was cost-effective compared to laboratory-based VL testing, which requiring 2-3 weeks turnaround.(27) POC VL testing enables real-time targeted ART adherence counseling but has not been evaluated among pregnant and postpartum women, for whom viral suppression is important not only for their own health, but also to reduce the likelihood of vertical HIV transmission.

In the Kingasa study, women randomized to have POC VL at enrollment, delivery and 6 months postpartum, will have a finger prick to obtain whole blood for the Cepheid Xpert HIV-1 RNA cartridge on the Xpert IV machine with results in 90 minutes. Women who are randomized to POC VL who have VL >200 c/ml will receive additional adherence counseling, following the STREAM protocol, [26] to address the challenges that they are having with ART use. At the delivery visit, infants of women in the POC VL arm will also have viral load testing done.

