## *Objectives*

**Aim 1: To determine the proportion of male partners of pregnant HIV-positive women who test for HIV at the clinic, based on invitation to a wellness visit (dual syphilis and HIV rapid test, blood pressure, visual acuity screening and COVID symptom screening, and if available, PCR testing for those with symptoms) compared to the standard of care (standard of care invitation letter for HIV fast track testing at the clinic).**

Innovations are needed to address the challenges associated with male partner engagement during their partner's antenatal and postpartum care periods. Provision of wellness visits providing STI testing and general health services, may overcome male partners reluctance to be tested in PMTCT clinics. We will randomize women 1:1 to the intervention and control arm and determine the proportion of male partners who test for HIV based on male enrollment numbers and data on HIV testing.

Primary outcome: The proportion of male partners who test for HIV compared by arms (comparing Arms 1 and 2 combined to Arms 3 and 4 combined).

**Aim 2: To evaluate whether POC viral load testing with same day ART adherence counseling improves ART continuation, and viral suppression among pregnant women living with HIV.**

Point-of-care viral load (POC VL) testing has been demonstrated to enable task-shifting and real-time adherence counseling. It is innovative to utilize POC VL for pregnant and post-partum women for real-time assessment of ART adherence, to improve ART use, retention in care, and viral suppression post-partum.

We will assess POC viral load monitoring and targeted ART adherence counseling compared to the standard of care laboratory-based HIV RNA testing, (comparing arms 1 and 3 combined to Arms 2 and 4 combined). Primary outcomes are viral suppression and HIV status disclosure at 6 months post-partum. *Hypotheses: POC viral load testing and same day adherence counseling will increase ART continuation and viral suppression*

Primary outcome: The proportion of HIV-positive women who are virally suppressed at 6 months post-partum. Viral suppression will be defined as plasma viral load <50 copies/ml.

**Aim 3: To evaluate whether engagement in care is improved among male partners who are provided a phone call follow up from a male counselor after HIV testing compared to standard of care.**

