Brief study questionnaires will be administered will occur at the PMTCT visits to avoid separate study-specific visits. Postnatal care and infant immunization visits will follow the routine maternal and child health (MCH) schedule. Viral load (VL) monitoring will include POC VL testing at enrollment, delivery, and every 6 months until M6 post-partum for women randomized to the intervention arm, and laboratory HIV RNA testing at enrollment, and every 6 months until M6 post-partum for women randomized to the control arm. Blood samples will be batch-tested at collaborating laboratories. Women will be asked about interruptions in ART use. If the mother is stable on ART with good adherence and undetectable VL, post-partum visits will be scheduled for week 6, and months 3 and 6. During these clinic visits, women will complete interviewer-administered surveys to collect data on behavioral factors that could mediate women's post-partum ART use. Women in the intervention arm will be provided their viral load results at that visit, and in the control arm will receive their viral load results at their next visit, in addition to counseling about the relationship between adherence, viral load and transmission risk.

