## Management of Viral Load Results

Participants in the intervention arm will have all routine ART monitoring tests performed according to the schedule described in the SoC arm follow-up procedures, however the POC VL assays will be utilized instead of lab based VL testing. POC VL testing will be performed using Cepheid's GeneXpert® HIV-1 VL assay performed at the beginning of the clinical encounter, so the clinical examination can be performed during the 90 minutes required to run a GeneXpert HIV VL test. If the participant is not able to wait for the results, then the study team will allow the participant to leave the study clinic but will ask them to remain in the vicinity and return to the clinic for their VL results. Prior to consent and enrollment, all potential participants will be counseled on the study procedures to ensure participants are able to comply with Intervention Arm study procedures, including potentially spending more time in clinic to receive VL results than they normally would as part of SoC clinic procedures. The GeneXpert testing will be conducted in the adjacent clinic site laboratory. Results will be managed according to SoC South African guidelines.

The clinical decisions from the SOC VL testing will adhere to the Ugandan guidelines. The algorithm for the current VL monitoring guidelines is summarized below:

- HIV VL <50 copies/mL: Reinforce the importance of good ART adherence and continue routine VL monitoring
- HIV VL 50-999 copies/mL: Provide standard of care ART adherence counseling, provide ART,

and ask participant to return to the clinic in six months for repeat VL testing. If the VL remains high (50-999 copies/mL) upon repeat testing, then the participant should continue receiving enhanced adherence counseling and repeat VL testing every six months until viral suppression (<50 copies/mL) is achieved.

- HIV VL  $\geq 1,000$  copies/mL: Provide standard of care ART adherence counseling; provide ART and ask participant to return to the clinic in three months for repeat VL testing. If the VL remains high ( $\geq 1,000$  copies/mL) after repeat testing, then participants will be considered for switching to second line treatment according to Uganda guidelines.

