#### HIV seroconversion

Study staff will counsel male partners who seroconvert and refer them to local HIV care providers for ongoing-care and initiation of antiretroviral therapy according to Uganda treatment guidelines. Seroconverters will be asked to remain in the study until completion of the follow up period in order to implement data collection relevant to secondary outcomes -- antiretroviral resistance, POC plasma VL testing and CD4 after HIV seroconversion.

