**Table 5. Procedures for HIV-positive pregnant women**

	ANTENATAL				Delivery	POSTNATAL	
	T1	T2	T3	T4		M3	M6
ADMINISTRATIVE AND REGULATORY PROCEDURES							
Obtain written informed consent	[X]	[X]	[X]	[X]			
Assign participant identification number	[X]	[X]	[X]	[X]			
Assess eligibility	[X]	[X]	[X]	[X]			
Collect/update locator information	[X]	[X]	[X]	[X]		X	X
Collect/update demographic information	[X]	[X]	[X]	[X]			
Obtain random allocation	[X]	[X]	[X]	[X]			
Schedule next visit	[X]	[X]	[X]	[X]		X	X
COUNSELING							
HIV/STI risk reduction counseling, condom provision	[X]	[X]	[X]	[X]		X	X
Standard of care counseling (ART adherence, clinical & prevention benefits)	[X]	[X]	[X]	[X]		X	X
CLINICAL PROCEDURES							
Provide HIV test results	[X]	[X]	[X]	[X]			
Medical history	[X]	[X]	[X]	[X]		X	X
Perform physical exam	[X]	[X]	[X]	[X]		[X]	[X]
STI syndromic assessment and management	[X]	[X]	[X]	[X]		[X]	[X]
Referral for / provision of ART according to national guidelines	[X]	[X]	[X]	[X]		X	X
PMTCT PROCEDURES*							
Antenatal care package	[X]	[X]	[X]	[X]			
Postnatal care package						[X]	[X]
Infant HIV status at 6 weeks						X	
LABORATORY PROCEDURES							
Syphilis testing	X	[X]	[X]	[X]			
HIV serology	X	[X]	[X]	[X]			
Plasma HIV viral load (control arm)	[X]	[X]	[X]	[X]			X*
POC viral load (intervention arm) with same day ART adherence counseling	[X]	[X]	[X]	[X]	X		X

\*Standard of care

Study staff will perform study specific procedures at collaborating clinics

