**Table 7. Procedures for HIV seroconverters among HIV-negative male partners who initiate PrEP**

	Possible seroconversion visit ( $\geq 1$ rapid HIV test positive)	Follow-up to possible seroconversion (ideally within one month of possible seroconversion)	M3	M6
ADMINISTRATIVE, BEHAVIORAL AND REGULATORY PROCEDURES				
Provide HIV counseling, including couples counseling	X	X	X	X
CLINICAL PROCEDURES				
Collect medical history	X	X		X
Perform physical exam	X		X	X
Collect blood specimen	X	X	X	X
Stop PrEP, if applicable	X			
Provide test results	X	X		
Refer for HIV care		X		
Assess linkage to care			X	X
LABORATORY PROCEDURES				
CD4 count	X	X	X	X
POC HIV plasma viral load with ART linkage and adherence counseling	X	X	X	X
HIV serology (confirmatory EIA)	X			

HIV-negative men who seroconvert to HIV will have one set of samples collected as close in time to the seroconversion visit as possible (ideally, either at the SC or SC<1 month visits). Samples to be collected are:

CD4 count  
Viral load

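### The Aim 2 endpoint is defined on plasma, but the only specimen the protocol names for women in the POC groups is finger-prick whole blood

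*Protocol*

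**What the plan says.** - **Objectives, Aim 2.** The primary outcome is the proportion of women suppressed at 6 months post-partum, and "Viral suppression will be defined as plasma viral load <50 copies/ml".
- **POC HIV Viral Load (Background & Rationale).** Women randomized to POC testing at enrollment, delivery and 6 months "will have a finger prick to obtain whole blood for the Cepheid Xpert HIV-1 RNA cartridge on the Xpert IV machine". The sentence sits in the background chapter but describes a procedure of this trial. The only cut-off given with it is 200 copies/ml, which triggers extra adherence counseling.
- **Management of Viral Load Results.** In the intervention arm the monitoring schedule follows standard of care, "however the POC VL assays will be utilized instead of lab based VL testing". No specimen is named.
- **Antenatal and postnatal care.** The control arm has "laboratory HIV RNA testing at enrollment, and every 6 months until M6 post-partum for women randomized to the control arm". A further sentence sends blood samples to collaborating laboratories for testing in batches, without naming arm, visit or specimen.
- **Table 5.** One row reads "Plasma HIV viral load (control arm" and is marked at month 6. The other reads "POC viral load (intervention arm) with same day ART adherence counseling", with no specimen.
- **Table 2.** HIV RNA testing at 6 months post-partum is listed for HIV-positive women in serodiscordant couples, again without arm or specimen.

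**The concern.** The endpoint is a threshold on plasma. If the text is followed, control women are classified on plasma and POC women on finger-prick whole blood. Specimen is then tied completely to randomized group, so any disagreement between the two near 50 copies/ml is differential by arm. An intention-to-treat analysis does not remove that kind of error.

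This point is about the specimen. It would remain if every woman were tested on the same assay platform. It is also not something a statistical analysis plan could repair afterwards: if no plasma is taken from POC women at 6 months, no analysis rule recovers the value that the definition calls for.

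**Working it through.** **Step 1: is a plasma value planned for POC women at 6 months?**

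| Section | Who | Specimen |
|---|---|---|
| Objectives, Aim 2 | all women, endpoint | plasma |
| POC HIV Viral Load | POC groups, 6-month visit included | finger-prick whole blood |
| Management of Viral Load Results | POC groups | not named; POC replaces laboratory test |
| Table 5, month 6 | control group | plasma |
| Table 5, month 6 | POC groups | not named |
| Antenatal and postnatal care, batch testing | not stated | blood, type not stated |
| Table 2, 6-month HIV RNA | women in serodiscordant couples, arm not stated | not named |

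No entry assigns plasma, a parallel laboratory test or a whole-blood threshold to POC women. Two entries (batch testing and Table 2) are too loosely worded to exclude one.

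**Step 2: reproduce the plan's own figure.** Inputs: four arms of 50 (Figure 3), so n = 100 per group for the POC comparison; two-sided alpha 0.05, 80% power, and control suppression of 60%, 70% or 80% (section on power for viral suppression). No dropout and no continuity correction.

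Power = Φ[(d − 1.96·s0)/s1], where d = p2 − p1, s0 = √(2·p̄(1 − p̄)/n) and s1 = √([p1(1 − p1) + p2(1 − p2)]/n).

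The differences giving 80% power are 18.25, 16.3 and 13.4 points, which round to the plan's 18, 16 and 13. At the rounded values power is 79.0%, 78.4% and 77.1%. The plan's figures stand and are not in dispute.

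For 80% versus 93%: p̄ = 0.865, s0 = 0.0483, s1 = 0.0474, so Φ[(0.13 − 0.0947)/0.0474] = Φ(0.74) = 0.771.

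**Step 3: sensitivity, on assumed misreading.** The documents give no whole-blood/plasma agreement, so m is an assumption. Let a share m of plasma-suppressed POC women be read at or above 50. Observed POC suppression is then p2(1 − m).

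| m | observed, 80% vs 93% row | difference (points) | power | power, 70% vs 86% | power, 60% vs 78% |
|---|---|---|---|---|---|
| 0 | 0.930 | 13.0 | 0.771 | 0.784 | 0.790 |
| 0.02 | 0.911 | 11.1 | 0.612 | 0.674 | 0.707 |
| 0.05 | 0.884 | 8.3 | 0.365 | 0.489 | 0.565 |
| 0.10 | 0.837 | 3.7 | 0.100 | 0.219 | 0.327 |

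With no true effect at 80% suppression, the same m gives observed values of 0.784, 0.760 and 0.720. The two-sided rejection rate is then 5.9%, 10.5% and 26.2% instead of 5%, with POC appearing worse.

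**Step 4: the opposite error.** Let a share m of unsuppressed POC women be read below 50, so observed suppression is p2 + (1 − p2)m. In the 80% versus 93% row, m = 0.05 and 0.10 give 0.9335 and 0.937, with power 0.798 and 0.823. With no true effect the rejection rate across the three rows is 5% to 9%, with POC appearing better. At equal m this error matters less, because fewer women are unsuppressed.

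**The case against.** The strongest reply is that the mismatch rests on one sentence in a background chapter. The operational section and the POC row of Table 5 name no specimen. The batch-testing sentence and the 6-month HIV RNA entry in Table 2 are not limited to one arm. The asterisk on the month-6 plasma cell of Table 5 is explained once as standard of care and once, in the legend, as covering POC testing in one arm and laboratory testing in the other. A classification rule could also sit in an analysis plan or laboratory manual that is not shown.

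Much of this stands, and it limits what can be claimed:

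- A reader might infer that POC women will certainly have no value meeting the definition. The text does not go that far; it leaves room for a qualifying sample. But it plans none explicitly, and replacing the laboratory test points the other way.
- A reader might infer a direct contradiction with HIV seroconversion, which mentions "POC plasma VL testing and CD4 after HIV seroconversion", and with Table 7, which lists "POC HIV plasma viral load with ART linkage and adherence counseling". Both concern male partners who seroconvert, not the randomized women. They show only that the protocol elsewhere describes POC testing on plasma.
- A reader might infer that whole blood will make the POC groups look worse. The documents support no direction: cells in whole blood might raise a reading, while a small finger-prick volume might miss a low one.

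The reply does not remove the mismatch. The sentence in question states what will be done in this trial at the endpoint visit, and nothing in the operational sections replaces it.

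**Conclusion.** The point holds in limited form. As written, the Aim 2 endpoint is defined on plasma, the only specimen named for POC women is finger-prick whole blood, and the specimen therefore differs by randomized group. This is a defect in the primary endpoint's measurement that is cheap to correct beforehand and cannot be recovered if no plasma is taken.

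The size is not derivable from the documents. The power loss from 77% to between 61% and 10%, and the null rejection rate of up to 26%, rest on assumed misreading of 2% to 10% in one direction only, with 100 women per group and no dropout. The 10% figures are the end of that assumed range, not an expectation. They show only that, with a trial sized for differences of 13 to 18 points, modest disagreement confined to one group would matter.

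**What to change.** Reconcile POC HIV Viral Load, Objectives (Aim 2), Antenatal and postnatal care, Management of Viral Load Results, Table 2 and Table 5, so that the 6-month post-partum endpoint value comes from the same specimen in both groups. State which arm and specimen the batch-testing sentence and the Table 2 entry cover.

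Plasma is the simplest choice: it matches the existing definition and is what Table 5 lists for control women. Finger-prick POC testing could still be used for the same-day counseling result. If whole blood is kept for the endpoint, amend the definition under Objectives to say how a whole-blood POC result is classified as suppressed or not; the specimen would then still differ by group, and the report should say so.

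The cost is protocol wording and, for plasma, a venous sample with plasma separation for POC women at the endpoint visit. The text following Table 2 already foresees six-monthly laboratory monitoring, so part of that draw may already be planned, although it does not say for which women.
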